## **6. Study Location**

### **6.1 Location**

The MRC/Wits Agincourt Research Unit oversees the maintenance and operation of the Agincourt Health and Demographic Surveillance Site (HDSS). Roughly 500km northeast of Johannesburg, the unit has been engaged in population-based health and demographic research since 1992. Strong ties with the local community ensure the continual functioning and sustainability of the research.

Constituting a sub-district of the Bushbuckridge district, the Agincourt study site consists of 420 km^2 of semi-arid scrubland with low rainfall, poorly-suited for subsistence farming though used for game farming and low-density cattle rearing. The study area contains six government run clinics, a private community health centre, and one larger area public health centre with patients being referred to three district hospitals, each located at 25- 55 kilometers from the site and relying on namely public means for transport.

### **6.2 Study Population**

The Agincourt HDSS population is comprised of roughly 120,000 individuals- mainly xiTsonga-speaking- spread throughout 20,000 households in 31 research villages. Roughly one-third of the permanent HDSS population is comprised of former Mozambican refugees, who immigrated to South Africa during the 1980s. Our population of focus will include traditional healers living in this region, their patients, and health care workers providing services at local health facilitates.

## **7. Data Management and Analysis**

### **Data Management**

#### **Quantitative data:**

Questionnaires, observations of training, as well as HIV testing data will be collected and uploaded to a REDCap database which is housed at Vanderbilt University. REDCap provides automated export procedures for seamless data downloads to Excel and common statistical packages (SPSS, SAS, Stata, R), as well as a built-in project calendar, a scheduling module, ad hoc reporting tools, and advanced features, such as branching logic, file uploading, and calculated fields. It also provides additional security options, including the ability to restrict a user's ability to download data tagged as identifiers to further protect participant privacy.

Study participants will be assigned a unique, coded identification number at the time of study enrolment. In order to maintain participant confidentiality, all laboratory specimens, study case report forms, and reports will be identified using that coded number. Only research staff will have access to the coded number. Key study personnel, including Drs. [name] and [name], will store research data, including medical and laboratory records, in locked cabinets and all e-files will be password protected. Data will be stored in password-protected files within secure buildings at the MRC/Wits Agincourt Research Unit's rural field offices. We have additional measures to enhance security when data are housed at Vanderbilt. Access to all data will be ID and password-protected, including data warehouse software and computers managing and analyzing survey data. No data will be released with any information that may directly or indirectly identify participants, their clinical information, or laboratory results to outside agencies.

### **Data Analysis**

Given that participants may complete none, one, two, or all three of these intervention components, we will consider four different intervention component variables to the Healer-Clinician HIV Prevention Collaborative intervention: (1) Uptake of healer-initiated HIV counseling and testing (vs. those who did not), (2) Participation in additional counseling sessions (vs. those

who did not), (3) Attendance at  $\geq 1$  Open House event at the health facility (vs. those who did not), and (4) An index ranging from 0 to 3 indicating the number intervention components completed.

The primary outcome among those testing HIV negative or refusing testing is uptake of health facility HIV testing within 6 months. We will operationalize the outcomes in the positive (e.g., tested at health facility within 6 months) such that the risk ratios (RR) for the intervention components will be  $>1.0$  if effective. We will estimate the association of each intervention component individually (numbers 1-3 above) using separate regression models that are each further stratified by potential modifiers such as gender, age, sexuality, immigration status, and other baseline characteristics. We will use *modified Poisson regression* models for each intervention component to estimate risk ratios and 95% confidence intervals.

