### Calculation of Sample Size & Sampling Strategy

We anticipate approximately 5%, perhaps 10%, of study participants will test positive for HIV and not be eligible for the analysis of health facility HIV testing within 6 months among those testing **HIV negative or refusing testing**. We further estimate that 70% will complete the healer-initiated HIV test, 60% will participate in additional counseling sessions, and 50% will attend an open house. Because study participants had no history of HIV testing in the prior year, we anticipate the primary endpoint of uptake of HIV testing at the health facility will be low, approximately 30%. Finally, given the importance of identifying sub-groups which may benefit the most from the intervention components, we have powered our study to detect significant associations within strata of potential modifiers (e.g., gender). We utilized Stata psim command to conduct 500 simulations each for all combinations of the parameters described above to estimate power to detect a range of RRs.

Given our sample size of 600 study participants, with 5% testing HIV+, and for a modifying variable distributed 50%/50%, we have ~90% power to detect stratum-specific RRs of 2.0 for each intervention component (Table 1). We still retain >80% power to detect RRs of 2.25 even if uptake of HIV testing in control group is as low as 20%. Similarly, if the modifying variable is distributed 40%/60%, we retain ≥80% power to detect stratum-specific RRs of 2.0 (Table 2). Thus, the high power due to our sample size allows for robust assessment and identification of intervention associations within key subsets of participants (gender, stigma, etc.).

Given that we only anticipate 10-30 participants to test HIV+, we will be underpowered to detect a meaningful association for how the intervention components associate with uptake of ART services at the health facility within three months among those testing **HIV positive**. However, the proportion testing positive, the proportion linking to ART care, and the magnitude of the RR for the intervention components will provide important preliminary data for whether this intervention improves ART care and retention, and not just linkage to HIV prevention services (such as follow-up HIV testing in those who are negative).

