## 5. Methods

## Measurement of Results

*Community member (those offered HIV testing) and healer outcomes:* Participants will complete both a baseline and 7-month post-enrollment questionnaire using the ACASI-system on a tablet. Data collection at 7 months will include the baseline survey and additional questions about uptake of HIV testing outside of the study and feedback about the acceptability and satisfaction with the study experience. These will be conducted by a study assistant based in the Agincourt area who is fluent in English and xi-Tsonga. The number of participants approached, the number who agree to testing and counseling (including testing outcome), and reports on the impact of performing HIV testing and counseling on healer income will be collected by the traditional healer. Health clinic research staff will collect uptake of testing during one of the “Open House” events and during non-open house days (if, for example a patient seeks testing during regular clinic hours). Clinical data will be accessed using “Clinic Link” which allows us to gain access to relevant clinical data, including ART uptake and retention in care. Data from clinical providers who participate in the stigma reduction intervention will complete surveys at study initiation and immediately after the study has concluded.

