Baseline	Enrollment	Demographics, HIV Stigma, Trust in allopathic provider, belief in HIV test, use of traditional medicine, perceived risk of HIV
Baseline	Healer-initiated C&T, including stigma reduction	Attendance, HIV status, enrollment in care and treatment if positive
Month 6	HIV re-test	Attendance, HIV status, enrollment in care and treatment if positive
Month 7	Follow-up survey & qualitative questions	HIV Stigma, Trust in allopathic provider, belief in HIV test, use of traditional medicine, perceived risk of HIV, experience with the healer-clinician collaborative

Table 6: Project Activities and Data Collection Points

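### Open House attendance (component 3) can overlap with the primary outcome, so its risk ratio above 1.0 cannot by itself be read as an Open House effect

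*Combined protocol and SAP*

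**What the plan says.** **Exposure.** Section 7, Data Analysis, lists four intervention variables. The third is attendance at one or more "Open House event at the health facility (vs. those who did not". The fourth is a 0-3 count of components completed, so it contains the third.

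**Outcome.** The same section states: "The primary outcome among those testing HIV negative or refusing testing is uptake of health facility HIV testing within 6 months". The sample size text in Section 4 uses the same window; participants who test positive will "not be eligible for the analysis of health facility HIV testing within 6 months among those testing" negative or refusing.

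**Capture of tests.** Section 5, Measurement of Results (repeated under Data Collection), has the clinic's research team log tests taken at Open Houses as well as those taken on other days: "events and during non-open house days (if, for example a patient seeks testing during regular clinic hours". Both settings are therefore recorded as facility testing.

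**Model and direction.** "We will estimate the association of each intervention component individually (numbers 1-3 above) using separate regression models", by modified Poisson regression, stratified by baseline characteristics. Outcomes are coded positively "such that the risk ratios (RR) for the intervention components will be" above 1.0 if the components are effective. No model is named for the index.

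**Timing.** Table 3 words the endpoint as a facility test at 6 months. "Table 6: Project Activities and Data Collection Points" has a Month 6 re-test row and no row for Open Houses.

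**The concern.** Nothing in the plan removes Open House tests from the outcome or requires attendance to precede the test. Two things follow. First, a person tested at an Open House becomes exposed and a success in one visit, and a non-attendee cannot have such a test. Second, a person who tests in month 2 and attends in month 5 is counted as exposed with a good outcome, although attendance could not have caused that test.

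Either route can push the component 3 RR above 1.0 when Open Houses change nobody's testing. This comes from how the variables are defined, so stratifying or adjusting for baseline characteristics would not remove it. At stake is the interpretation of one of the three component estimates, and of any index result. Components 1 and 2 have no same-visit overlap of this kind.

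**Working it through.** **Inputs from the plan (Section 4):** 600 participants, 5% HIV positive, so 600 × 0.95 = 570 analysed; facility testing about 30%; Open House attendance 50%. **Not in the documents, so assumed:** the number of Open Houses, the share of tests taken at them, and the timing of attendance and tests.

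**0. The plan's own figure.** Table 1 gives power 0.928 for RR 2.0, stratum of 135, 30% baseline uptake and a 50% component. A two-proportion formula (67.5 per group, 0.30 vs 0.60, two-sided 0.05) gives 0.947. Simulating the robust log-RR test gives 0.939. The inputs are therefore read as the plan intends.

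**1. No effect; some tests happen to fall on event days.** Let T = 0.30 be overall uptake and s the share of tests on an event day. To hold attendance at 50%, background attendance is a = (0.5 − Ts)/(1 − Ts). Then P = P(attend | tested) = a + (1 − a)s and, because attendance is 50%, RR = P/(1 − P).

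| s | a | P | RR |
|---|---|---|---|
| 2% | 0.497 | 0.507 | 1.03 |
| 5% | 0.492 | 0.518 | 1.07 |
| 10% | 0.485 | 0.536 | 1.16 |
| 25% | 0.459 | 0.595 | 1.47 |

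With an assumed 126 clinic days in 6 months, 3, 6 or 12 event days give s = 2.4%, 4.8% or 9.5% and RR 1.03, 1.07 or 1.15. Pure coincidence therefore points to the low end.

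**2. No effect; attendance after the test.** The same formula applies, with s the share of otherwise non-attending testers who attend later: again 1.03, 1.07, 1.16 and 1.47.

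**3. Attendees test at the event; other testing is unchanged.** With p0 = 0.30 in non-attendees and a share q of attendees tested at the event, RR = [q + (1 − q)p0]/p0.
- q = 20%: (0.20 + 0.80 × 0.30)/0.30 = 0.44/0.30 = 1.47.
- q = 43%: (0.43 + 0.57 × 0.30)/0.30 = 0.601/0.30 = 2.00, the effect size highlighted in the power statement.

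By simulation, RR 1.47 is significant in 93% of runs at 570 people, and RR 2.00 in 94% at 135. These event tests may be a real benefit. The RR cannot show whether they are.

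**4. Two tempting repairs, both under no effect.**
- Moving people who attended after testing to the unexposed group. With even, independent timing, half of the 0.15 who both attend and test did so in that order. RR = (0.075/0.425)/(0.225/0.575) = 0.176/0.391 = 0.45, an immortal-time error.
- Recoding event tests as no test. RR = a/(1 − a): 0.485/0.515 = 0.94 at s = 10%, and 0.459/0.541 = 0.85 at s = 25%.

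**5. What a time-ordered analysis can show.** Simulated with truly additional event tests, an as-written RR of 2.00 (20% background uptake, 25% of untested attendees tested at the event) becomes about 1.00 with time-updated exposure, or 0.60 with a month-3 landmark that keeps event tests. An as-written 1.47 (30% and 20%) becomes about 1.00 or 0.76. These ratios address later testing and cannot show a same-visit benefit.

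**6. Precision around RR 1.0 at 570 people.** As written, exp(±1.96 × √[(0.7/0.3)(1/285 + 1/285)]) = 0.78 to 1.29. Time-updated, with 42.8 and 128.4 events, exp(±1.96 × √[1/42.8 + 1/128.4]) = 0.71 to 1.41, and slightly wider if follow-up ends at event tests. Landmark: 0.64 to 1.56.

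**The case against.** **The plan does not say that an RR above 1.0 proves effectiveness.** A reader might infer that it does. The sentence sets the direction of coding: if a component works, its RR will exceed 1.0. The converse is not stated, and the next sentence speaks of association. This stands, so the point concerns interpretation.

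**No sentence says that Open House tests count.** That is correct. It is inferred from the events being at the facility, from staff collecting tests there, and from the lack of any exclusion. The inference is reasonable, but it remains an inference.

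**The outcome may be the Month 6 re-test.** Table 3 and Table 6 allow that reading. Overlap would then be smaller, and attendance would mostly come first. Sections 4 and 7 say within 6 months, so the passages need reconciling; this does not dispose of the point.

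**The Limitations section already covers it.** It does not. It says that a non-randomised pilot cannot compare healer-initiated testing with other modalities, which is a different limitation. Conversely, a reader might infer that a misread component 3 RR will feed into the later randomised trial. Limitations names no component RR among the elements for that design, so the documents do not support that step.

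**The bias may be trivial.** Coincidental RRs of 1.03 to 1.16 lie well inside the as-written interval of 0.78 to 1.29. This stands for coincidence alone. It does not cover deliberate testing at events.

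**Dates are probably collected anyway.** Table 6 is a summary, and its silence does not show that dates will go unrecorded. The plan should still list them.

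**Conclusion.** The point holds as one of definition and interpretation. As written, a component 3 RR above 1.0 may reflect an Open House effect, same-visit testing, or attendance after the test, and the planned model cannot separate them. Any analysis of the index inherits this.

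The size cannot be determined from the documents. With 30% uptake and 50% attendance, the no-effect RR runs from 1.03 to 1.47 for assumed shares of 2% to 25%. It is 1.47 or 2.00 if 20% or 43% of attendees test at the event with other testing unchanged. It would be 1.00 if attendance is unrelated to intention to test and event tests only replace other tests.

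A reader might infer that the component 3 RR is wrong or wholly artefact. The documents do not support that: if event tests are truly additional, an RR above 1.0 is real. Confidence is high for the overlap in the definitions, and low for any particular size.

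**What to change.** In Section 7, Data Analysis:

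1. State whether tests taken at Open Houses count toward the primary outcome. Reconcile the 6-month wording in Table 3 and the Month 6 re-test in Table 6 with the within-6-months wording in Sections 4 and 7.
2. Record Open House attendance dates, facility test dates, and a flag for tests taken at an Open House.
3. Report tests at Open Houses (number and percent of attendees) separately from other facility tests.
4. Do not treat attendance after the first facility test as exposure to that test. Do not implement this by simply moving late attenders to the unexposed group, or by recoding event tests as no test.
5. Label the as-written component 3 RR, and any index result, a descriptive association that includes same-visit testing.

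A time-updated or landmark ratio is an optional sensitivity analysis. If it is used, say that it addresses later testing only, and that the time-updated version is a rate ratio rather than the planned risk ratio.

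**Cost.** Slightly more data capture; staff already collect testing in both settings, so the flag is a small step. The component 3 RR gets a less favourable reading, and the optional ratios have wider intervals.

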**Table 1.**

Stratum specific sample size*	Baseline uptake of health facility HIV testing	Intervention component distribution	Power for relative increase in HIV testing uptake among those with the intervention component vs. those without		
			RR=1.75	RR=2.0	RR=2.25
135	20%	40%	0.484	0.702	0.856
		50%	0.458	0.724	0.868
		60%	0.432	0.622	0.824
		70%	0.346	0.576	0.762
135	25%	40%	0.628	0.852	0.954
		50%	0.596	0.832	0.952
		60%	0.604	0.814	0.964
		70%	0.501	0.708	0.874

135	30%	40%	0.772	0.924	0.994
		50%	0.738	0.928	0.996
		60%	0.726	0.924	0.998
		70%	0.592	0.850	0.976
135	35%	40%	0.868	0.990	1.000
		50%	0.832	0.974	1.000
		60%	0.830	0.980	1.000
		70%	0.744	0.952	0.996
135	40%	40%	0.922	1.000	1.000
		50%	0.924	1.000	1.000
		60%	0.932	1.000	1.000
		70%	0.852	0.990	1.000

\*N=135 assumes ~10% test HIV+ and are excluded and the remaining participants are divided equally into two strata of a modifier (e.g., 50% female)

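### A rising trend in the 0–3 component count cannot by itself be read as each added component helping, and the planned separate models do not reliably settle it when components overlap

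*Combined protocol and SAP*

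**What the plan says.** The Data Analysis section lists four exposure variables. Three are yes/no indicators: healer-initiated testing, extra counseling and attending an Open House. The fourth is "An index ranging from 0 to 3 indicating the number intervention components completed", an unweighted sum of the other three.

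The modelling text covers the first three: "We will estimate the association of each intervention component individually (numbers 1-3 above) using separate regression models", each stratified by potential modifiers and fitted by "modified Poisson regression" to give risk ratios with 95% confidence intervals. The section does not say:

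- whether the index enters as a linear term or as categories;
- whether the component models adjust for one another;
- how an index association will be interpreted, or whether equal component effects will be checked.

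The sample-size section expects that "70% will complete the healer-initiated HIV test, 60% will participate in additional counseling sessions, and 50% will attend an open house", with facility testing of about 30%. It does not say how far uptake of the components overlaps.

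**The concern.** The index is the only planned variable that describes the programme as a whole. Index 1 pools people who had only the healer test, only counseling or only an Open House; index 2 pools the three possible pairs. The natural reading of a rising trend is that each extra component raises facility testing. That reading needs the three components to have similar risk ratios.

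The protocol gives a reason to doubt this. Under Measurement of Results, clinic staff record testing done at Open House events, so the Open House is itself an occasion for the primary outcome. The other two components are not.

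The Limitations section says the pilot's data will inform a larger randomized trial. If the index and the single-component models agreed for the wrong reason, inert components could look worth carrying forward.

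**Working it through.** **Inputs.** From the sample-size section: uptake 70/60/50% for healer test (H), counseling (C) and Open House (O); 30% facility testing, used here as the risk with no component; RR 2.0 for an active component; 600 participants with 5% testing positive, so 600 × 0.95 = 570, or 285 in each half. Table 1 uses strata of 135 ("N=135 assumes ~10% test HIV+ and are excluded and the remaining participants are divided equally into two strata of a modifier"). However, 600 × 0.90 / 2 = 270, a separate discrepancy that needs reconciling. Assumptions: multiplicative effects, a two-sided 5% test, and the overlap patterns named below.

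**The plan's own figure.** Table 1 gives power 0.928 for n = 135, 30% baseline, 50% with the component and RR 2.0. A two-proportion formula with 67.5 per group gives Φ[(0.30 − 1.96 × 0.0856)/0.0816] ≈ 0.947. Simulating the Wald test on log RR gives 0.941. Across all 120 cells of Tables 1 and 2, that simulation is within 2 points in 104 and within the Monte Carlo error of 500 simulations in 115. The method therefore matches the plan's. The plan gives no figure for the index.

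**One active component (Open House RR 2.0), independent uptake.**

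- Index 0: share 0.3 × 0.4 × 0.5 = 0.06; testing 30%.
- Index 1: shares H 0.14, C 0.09, O 0.06; testing (0.14 × 0.3 + 0.09 × 0.3 + 0.06 × 0.6)/0.29 = 0.105/0.29 = 36%.
- Index 2: shares HC 0.21, HO 0.14, CO 0.09; testing (0.21 × 0.3 + 0.14 × 0.6 + 0.09 × 0.6)/0.44 = 0.201/0.44 = 46%.
- Index 3: share 0.21; testing 60%.

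A log-linear fit gives RR 1.28 per step. The trend is significant in about 99% of simulated trials at n = 570 and about 85% at n = 285. The index-0 group is 0.06 × 570 = 34 people, or 0.06 × 135 = 8 in a Table 1 stratum.

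**Opposite effects, independent uptake.** With RRs 0.67/1.0/1.5, testing by level is 30/28/28/30%, RR 1.01 per step, with 5–6% rejection. With RR 2 against 0.75, RR per step is 1.08–1.15 and rejection is 24–54% at n = 540 (600 × 0.90). Cancellation therefore needs near-reciprocal effects.

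**What the separate models show.** With independent uptake they give crude RRs of 1.0/1.0/2.0 in the first case, which is correct. With overlap, the crude RR of the inert healer test is [1 + P(O|H)]/[1 + P(O|not H)], because attending doubles the risk.

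| Overlap assumed | Attend Open House if H / if not H | Crude RR, healer test | Crude RR, counseling |
|---|---|---|---|
| Independent | 50% / 50% | 1.00 | 1.00 |
| Latent correlation 0.3 | 56% / 36% | 1.56/1.36 = 1.15 | 1.14 |
| Latent correlation 0.6 | 62.5% / 20.9% | 1.625/1.209 = 1.34 | 1.33 |
| Fully nested | 71% / 0% | 1.71 | 1.83 |

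The attendance figures at 0.3 and 0.6 are solved from the crude RR and the 50% overall attendance (for example, 0.7 × 0.56 + 0.3 × 0.36 = 0.50). At n = 570, rejection for the inert components is 24–82% over correlations 0.3 to 0.6. A joint model, log P(test) = β0 + β1H + β2C + β3O, brings it back to about 5%.

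**Precision of the joint model.** Sandwich standard errors, n = 570, independent uptake, RRs 1/1/2: 0.057 for log RR per index step, so 3 × 0.057 = 0.17 over three steps, against 0.17 for β1 + β2 + β3. At latent correlation 0.6, the standard error for the Open House log RR rises from 0.103 unadjusted to 0.115 adjusted.

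**Test of equal component RRs (2 df), RRs 1/1/2.** Power is 100% at n = 570 and 97% at n = 285 with independent uptake. At n = 135 it is only about 50–70%, depending on overlap.

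**The case against.** The strongest reply is that the plan does not rest on the index. The same section models each component separately. With independent uptake those models find the Open House in essentially all simulated trials and reject for the inert components in 4–7%. With RRs 0.67/1.0/1.5 they detect the negative effect in 83% and the positive one in 88% at n = 570. This stands, but only for independent uptake.

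Four further points also stand:

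- A count is a legitimate summary of engagement. Equal RRs are needed only for a per-component reading, which the plan does not state.
- The 99% is not a false-positive rate: all three versus none truly has RR 2.0 in that scenario, so the index is right to show an association.
- The rise is not always smooth. With fully nested uptake and only the Open House active, testing is 30/30/30/60%, a step that a categorical index would show.
- The documents expect RRs above 1, and no section says the index will choose the package for the later trial.

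A reader might infer that the index is invalid, that it hides component effects from the investigators, or that opposite effects always cancel. The documents and the arithmetic support none of these.

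**Conclusion.** The point holds in limited form. An index trend alone does not show that each added component helps: one active component at RR 2.0 is enough to give 30/36/46/60% and RR 1.28 per step. The planned separate models correct that reading if uptake is independent. At latent correlations of 0.3 to 0.6 they give inert components crude RRs of about 1.14 to 1.34, so index and single models could agree wrongly.

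This rests on assumed overlap, an assumed single active component and a 30% baseline. The one-active-component case needs no harmful effect and is the firmer ground; cancellation is a special case. Priority is minor to moderate, because the gap is in specification and interpretation and costs little to close.

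**What to change.** In the Data Analysis section:

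1. State the coding of the index and describe it as a descriptive count of engagement, with no per-component dose interpretation.
2. Add one modified Poisson model with all three component indicators. Report the mutually adjusted component RRs and the all-three-versus-none RR, exp(β1 + β2 + β3), beside the planned separate models.
3. Report the 2-df test of equal component RRs in the whole sample as supporting information only. Non-rejection, above all in small strata, does not license a dose statement.

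The cost is SAP wording and one extra model on data already collected. The all-three-versus-none interval is wider than the one printed for a single index step, though about as wide as that for three steps. Adjusted component intervals widen when components overlap. The model assumes no interaction, and with few people completing nothing the contrast leans on that assumption. Adjusted RRs also leave out any effect of an earlier component that acts through a later one, such as a healer test that leads someone to an Open House. That is why the separate models should stay.
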